5. STUDY PROCEDURES

5.1 Screening

The following procedures are performed during screening, staging and workup (Table 5.1, below). These procedures are to be performed within 4 weeks prior to study drug administration, except where indicated.

Table 5.1: Procedures During Screening, Staging and Workup

Procedures	Specifics
Informed consent	
Full History and Physical Examination	History – present illness, all surgeries, all other medical illnesses, review of systems, allergies, all prior therapy for cancer and concurrent meds; F Physical exam – record weight, and note abnormalities in any major organ system (including but not limited to neurologic, head and neck, lymph nodes, cardiovascular, pulmonary, abdomen, extremities), note and
	measure sites of disease
Vital signs (including temperature, pulse, and blood pressure)	
ECOG performance status	
Pregnancy test (females of child-bearing potential only)	At screening, within 2 weeks prior to first dose
Disease status (note: measurement of lesions assessed only by physical exam should be performed within 1 week prior to first dose)	Staging with bone marrow biopsy or aspirates.
Note: Bone marrow biopsy or aspirate within 4 weeks prior to first dose of drug in all patients. Cytogenetics, immunohistochemistry, and histochemistries performed as indicated.	Lumbar punctures or radiographic investigations as appropriate to the disease.
Serum chemistries (repeat if screening chemistries completed greater than 72 hours prior to the first dose)	Sodium, potassium, chloride, CO ₂ , blood urea nitrogen, creatinine, glucose, calcium, phosphate, magnesium, AST and ALT, total bilirubin, alkaline phosphatase, total protein, albumin, uric acid, lactic dehydrogenase
Urinalysis (including microscopic)	
CBC with platelets (repeat if screening test completed greater than 24 hours prior to the first dose)	
PT/aPTT	
Chest X-ray PA-LAT	
HIV, Hepatitis B and C	Results of test performed within past 3 months acceptable

PA-LAT = Posterior anterior - lateral.

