3.1 Inclusion Criteria

- A. Must be at least 18 years of age.
- B. Patients must have relapsed/refractory leukemias for which no standard therapies exist. Patients with poor-risk myelodysplasia (MDS) [i.e. refractory anemia with excess blasts (RAEB-1 or RAEB-2) by WHO classification] and chronic myelomonocytic leukemia (CMML) who failed prior therapy are also candidates for this protocol. Relapsed/refractory leukemias include acute non-lymphocytic leukemia (AML) by WHO classification (i.e. ≥ 20% blasts), acute lymphocytic leukemia (ALL), or chronic myelogenous leukemia (CML) in blast crisis. Patients with CML who are resistant to at least two tyrosine kinase inhibitors and have no standard stem cell transplant option are also eligible.
- C. ECOG performance status of 0-2.
- D. A female of childbearing potential must have a negative serum or urine pregnancy test at screening. Women of child-bearing potential (i.e., women who are premenopausal or not surgically sterile) must use acceptable contraceptive methods (abstinence, intrauterine device [IUD], oral contraceptive or double barrier device), and must have a negative serum or urine pregnancy test within 2 weeks prior to beginning treatment on this trial. Sexually active men must also use acceptable contraceptive methods for the duration of time on study.

- E. Must be able and willing to give written informed consent.
- F. In the absence of rapidly progressing disease, the interval from prior treatment to time of study drug administration should be at least 2 weeks for cytotoxic agents, or at least one week for noncytotoxic agents. Persistent clinically significant toxicities from prior chemotherapy must not be greater than grade 2.
- G. Patients must have the following clinical laboratory values unless considered due to leukemic organ involvement:
 - 1. Serum creatinine ≤ 2.0 mg/dl.
 - 2. Total bilirubin ≤ 1.5x the upper limit of normal unless considered due to Gilbert's syndrome or hemolysis.
 - 3. Alanine aminotransferase (ALT), and aspartate aminotransferase (AST) \leq 2.5x the upper limit of normal unless considered due to organ leukemic involvement (then \leq 5x the upper limit of normal).
 - H. Patients with active CNS disease are included and will be treated concurrently with intrathecal therapy. INCB018424 will not be administered by intrathecal route.

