3.2 Exclusion Criteria

Patients with any one of the following criteria will not be eligible for study participation:

- A. Uncontrolled intercurrent illness including, but not limited to uncontrolled infection, symptomatic congestive heart failure, cardiac arrhythmia, or psychiatric illness/social situations that would limit compliance with study requirements.
- B. Active heart disease including myocardial infarction within the previous 3 months, symptomatic coronary artery disease, arrhythmias not controlled by medication, or uncontrolled congestive heart failure.
- C. Current treatment or treatment within 2 weeks or 5 half-lives (whichever is longer) prior to the first dose of study medication with another investigational medication or current enrollment in another investigational drug protocol (unless there is evidence of rapidly progressive disease in which case a shorter interval from last therapy may be acceptable).
- D. Females who are pregnant or are currently breastfeeding.
- E. Patients receiving therapy with intermediate or high dose steroids greater than the equivalent of 10 mg prednisone per day are not allowed.

- F. Evidence of active hepatitis or human immunodeficiency virus (HIV) infection determined by screening laboratory test results or results within prior 3 months.
- G. Any unresolved toxicity equal to or greater than Grade 2 from previous anticancer therapy, except for stable chronic toxicities not expected to resolve, such as peripheral neurotoxicity.
- H. Incomplete recovery from any prior surgical procedures or had surgery within 4 weeks prior to study entry, excluding the placement of vascular access.
- Uncontrolled intercurrent illness or any concurrent condition that, in the Investigator's opinion, would jeopardize the safety of the patient or compliance with the protocol.

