- i. Bone marrow aspiration or biopsy will be taken during the screening phase (within 4 weeks of starting drug), and at start of Cycle 4 (± 7 days), Cycle 7 (± 7 days), and thereafter at start of each 6th subsequent cycle (+/- 7days). Evaluation will include staining for fibrosis and cytogenetics if abnormal prior to therapy. Cytogenetic studies will be repeated only in patients with abnormalities at baseline, on Day 1 of Cycles 4 and 7 and thereafter on Day 1 of each 6th subsequent cycle(+/-7days). If unable to obtain BM aspirate, cytogenetics may also be done on peripheral blood collected for PD/PK analysis.
- j. Instruct patient that the dose is to be taken at 12 hour intervals at approximately the same time each day. The first dose of each day should be taken in the morning.
- k. For Cycle 1, PK samples to be collected on Day 1 at pre-dose, 0.5, 1, 1.5, 2, 4, 6, and if possible 8 hours after administration of the morning dose of INCB018424. For Cycles 2 and 3, a PK sample will be collected at pre-dose on Day 1.
- I. For Cycle 1, plasma and whole blood PD samples will be collected on Day 1 at pre-dose and 2, hours after administration of the morning dose of INCB018424. For Cycles 2, 3, and each subsequent scheduled visit to MDACC, plasma and whole blood PD samples will be collected at pre-dose on Day 1. Final PD sample will be collected at End-Of–Study visit. Not all samples may be collected on all patients. See Appendix F.
- m. Adverse events (AEs) considered related to study medication must be followed until resolution, start of a different treatment therapy or no longer considered to be clinically relevant in the opinion of the investigator. During the treatment phase, AE assessment is required weekly at the local physician's office during 1st cycle of therapy. During the 2nd and 3rd cycles assessments are required every 4 weeks, and then every visit thereafter.
- n. Compliance should be checked at each scheduled clinical visit. Any unused drug in sealed bottles will be returned to Incyte or its designee. MDACC will follow internal procedures to destroy and dispose of unused drug in open/unsealed bottles.

Protocol Number 2007-0925 October 13, 2008 Page 17 of 36

o. End-of-Study procedures are to be completed if patient completes study or at anytime patient terminates treatment early in the study.

5.2.1 Cycle 1

5.2.1.1 Cycle 1 - Day 1

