6. RESPONSE DEFINITIONS

Patients will be assessed for efficacy at the end of each 28 day cycle of therapy, +/-4 days for the first 3 cycles, then 3 monthly thereafter.

6.1 Acute leukemias, MDS, CML-BP, CMML:

- 6.1.1 Complete remission: The patient must be free of all symptoms related to leukemia and have an absolute neutrophil count $\geq 1 \times 10^9 / L$ and platelet count $\geq 100 \times 10^9 / L$, and normal marrow differential ($\leq 5\%$ blasts) in a normo- or hypercellular marrow.
- 6.1.2 Partial remission: CR with 6-25% abnormal cells in the marrow or 50% decrease in bone marrow blasts.
- 6.1.3 CRp: As per CR but platelet count <100 x109/L.
- 6.1.4 Hematologic Improvement (HI)

Hematologic improvement should be described by the number of individual, positively affected cell lines (e.g. HI-E; HI-E + HI-N; HI-E+ HI-P + HI-N).

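### A blast fall caused by prior therapy can be scored as partial remission, because the baseline marrow need not follow the last prior dose

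*Combined protocol and SAP*

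**What the plan says.** **Baseline marrow.** Table 5.1 (section 5.1) requires "Bone marrow biopsy or aspirate within 4 weeks prior to first dose of drug in all patients". Footnote i of the study calendar (section 5.2) agrees and gives the next sampling time: "Bone marrow aspiration or biopsy will be taken during the screening phase (within 4 weeks of starting drug), and at start of Cycle 4", with a 7-day tolerance either way. Section 7.3 adds only that the sample is taken before dosing, during screening. Other baselines in Table 5.1 are kept recent. The CBC carries the instruction "repeat if screening test completed greater than 24 hours prior to the first dose", chemistries are repeated if older than 72 hours, and lesions measured by physical examination have a 1-week limit. The marrow has no repeat rule.

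**Prior therapy.** Inclusion criterion F (section 3.1) begins "In the absence of rapidly progressing disease, the interval from prior treatment to time of study drug administration" and continues "should be at least 2 weeks for cytotoxic agents, or at least one week for noncytotoxic agents". Exclusion criterion C (section 3.2) asks for 2 weeks or 5 half-lives, whichever is longer, after an investigational drug, "unless there is evidence of rapidly progressive disease in which case a shorter interval from last therapy may be acceptable".

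**Scoring.** Section 6.1.2 defines partial remission as "CR with 6-25% abnormal cells in the marrow or 50% decrease in bone marrow blasts". It does not name the marrow from which the decrease is measured. Partial response is one of the assigned categories in section 9.5.2.

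**Decision rule.** Section 9.1.1 assumes a 0% null rate and a 15% target, enrolls 10 patients per disease category, and goes to 30 if at least one responds.

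**The concern.** The marrow window is longer than the required interval from prior therapy, and the two are not tied together. The screening sample is the only scheduled pre-treatment marrow, so in practice it is the reference for a 50% decrease. If a patient has that marrow, then receives more of the previous regimen, then starts study drug, any blast fall due to the previous regimen lies inside the interval over which response is measured.

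A 0% null leaves no room for responses that arise without drug activity, and there is no control arm in which such responses would show. One misattributed partial remission among the first 10 patients is enough to open 20 further places in that disease category. After expansion, each one adds 1/30, or 3.3 percentage points, to a response rate whose target is 15%.

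**Working it through.** **1. The plan's own figures reproduce.** Inputs from section 9.1.1: n = 10, at least 1 response, null 0%, target 15%, then n = 30.

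- Power at 15%: 1 − 0.85^10 = 0.803 (stated 80%).
- Chance of passing at a true rate of 0%: 0.
- Half-width at n = 30: 1.96 × √(0.15 × 0.85 / 30) = 0.128 (stated 0.13).

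So a false expansion is impossible under the stated null, but only if every scored response is due to the drug.

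**2. Calendar overlap.** Marrow window of 28 days (Table 5.1, footnote i) minus the minimum interval from prior therapy (criterion F).

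| Prior therapy | Minimum interval | Days in which it can follow the marrow |
|---|---|---|
| Cytotoxic | 14 | 28 − 14 = 14 |
| Noncytotoxic | 7 | 28 − 7 = 21 |
| Either, rapid progression | none stated | up to 28 |

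These are days of opportunity, not a measure of bias.

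**3. A compliant sequence.** Marrow on Day −27, last cytotoxic dose on Day −15, first study dose on Day 1. The marrow is inside its window and the cytotoxic interval is met. The prior drug was last given 12 days after the reference marrow. The patient is eligible and without a protocol deviation, so the exclusions from response assessment in section 9.5.2 do not apply.

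**4. Effect on the go decision.** Let q be the probability that a patient on an inactive drug is scored as a partial remission through carry-over. The documents give no value, so q is an assumption. P(at least 1 of 10) = 1 − (1 − q)^10:

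| Assumed q | Probability that the arm expands |
|---|---|
| 1% | 1 − 0.99^10 = 9.6% |
| 2% | 1 − 0.98^10 = 18.3% |
| 5% | 1 − 0.95^10 = 40.1% |

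This applies to patients scored under section 6.1. The criteria in section 6.2, used for chronic-phase CML, have no 50%-decrease limb.

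**The case against.** The case against rests mainly on rarity, and much of it stands.

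- **Selection.** Entry requires relapsed or refractory disease, or failed prior therapy. The waiver of the interval applies only when disease is progressing rapidly, where the earlier drug is evidently not clearing blasts. The widest calendar overlap is therefore where a carried-over response is least likely.
- **Timing.** The first scheduled on-treatment marrow is at the start of Cycle 4, about 12 weeks in. A carried-over fall must last that long or be caught on an unscheduled marrow. Under section 4.4, patients without objective response after 2 cycles may already have stopped, unless there is clinical benefit. Against this, responses are assessed from Day 1 of Cycle 2 and the statistical assessment is after 8 weeks (section 4.1), so the protocol expects response calls before the Cycle 4 marrow.
- **Wording of 6.1.2.** The sentence can be read as requiring the other remission conditions, including blood counts, in both limbs. Carry-over would then be rarer. The text supports a stand-alone 50% limb equally well.
- **Judgement and records.** Section 4.2 speaks of benefit considered significant, and prior therapy is recorded, so affected patients could be identified. But no scoring rule uses that record, and section 9.1.1 simply counts responses.

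A reader might also infer that hematologic improvement is inflated, because baseline counts may sit in a post-chemotherapy trough. The documents do not support adding that here. Exclusion criterion G limits entry with unresolved Grade 2 or higher toxicity, and hematologic improvement is not a response category in section 9.5.2.

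**Conclusion.** The gap is in the text and nothing closes it: a blast fall due to the previous drug can be scored as partial remission in a fully compliant patient. The design is sensitive to even a low rate of such events, with a false expansion probability of 9.6% to 40.1% per arm for an assumed q of 1% to 5%. Those figures assume an inactive drug, independent patients and the same q throughout an arm scored under section 6.1. The size of q is unknown and probably small, for the reasons just given.

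Two stronger readings should be avoided. A reader might infer that carry-over will routinely be counted as response. The documents show only that it can be, in patients treated after their screening marrow. A reader might also compound the per-arm figure over all four disease categories, but the CML category includes chronic-phase patients whose criteria contain no relative-decrease limb.

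The point merits a wording change before responses are scored. It does not call the sample size into question.

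**What to change.** - **Section 6.1.2:** define the reference as the last marrow before the first dose of study drug. State that the 50%-decrease limb may not be used if any antileukemic therapy was given between that marrow and first dose. Such patients count as responders only on the absolute criteria.
- **Table 5.1, footnote i and section 7.3:** state that the screening marrow should, where possible, be taken after the last prior antileukemic dose and within the same 4 weeks. Do not mandate a repeat marrow.

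The prior-therapy intervals, eligibility, dosing and sample size are unchanged; power stays at 0.803 and the half-width at 0.128. The cost is protocol wording, plus the loss of the 50% limb for a few patients whose screening marrow predates their last therapy.

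The change narrows the bias without eliminating it. A marrow taken shortly after the last prior dose satisfies the rule, yet cytoreduction from that dose may continue afterwards. An absolute level reached partly through the earlier drug would also still count. A compulsory later marrow could add a procedure for some patients and would not fully remove the late effect.

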5.2 Study Procedures

•	Screening Phase	Treatment Phase								End of Treatment		
Visit	Day -28 to Day -1	Cycle 1			Cycle 2+3			Subsequent Visits - For details see Footnotes		1		
		Day 1	Day 8	Day 15	Day 22	Day 1	Day 8	Day 15	Day 22	Day 1	Day 15	End of Study ^o
Evaluation – All evaluations have a												•
+/- 2 day window except for bone												
marrow biopsy (see footnote i).												
Informed consent ^a / Eligibility criteria	X	X										
Medical & medication history ^b	X	X	X	X	X	X				X ^b		X
Physical examination ^c	X	X	X	X	X	X				X ^c		X
Vital signs ^c	X	X	X	X	X	X				X ^c		X
Overall Response assessment (IWG-MRT) ^d						X				X ^d		X
ECOG performance status ^e	X					X				Xe		X
Concomitant medication review ^f		X	X	X	X	X				X ^f		X
Clinical laboratory tests ^g	X		X	X	X	X		X		X ^g		X
CBC ^h	X		X	X	X	X	X	X	X	X ^h	X^h	X
PT/PTT	X											
CXR	X											
Pregnancy test ^g	X											
FSH test ^g	X											
Serology / HIV laboratory tests ^g	X											
Urinalysis ^g	X											
BM aspiration, biopsy and cytogenetics ⁱ	X									Xi		
Administer 1st dose of INCB018424 ^j		X										
Dispense INCB018424 study medication ^j		X				X				X ^j		
PK sampling ^k		X				X						
PD biomarker sampling ¹		X				X				X ¹		X
Adverse event / Intercurrent illness assessment ^m		X	X	X	X	X				X ^m		X
Study medication compliance ⁿ			X	X	X	X				X ⁿ		X

- a. Informed consent must be obtained at Screening. At Screening and Day 1, assess eligibility for study entry and review eligibility for study entry on Day 1.
- b. Medical history will be done at each visit. Medication history will be obtained only at the screening visit.
- c. A complete examination will be performed at Screening and the End-of-Study Visit . A "targeted" examination will be performed at all other visits. During the treatment phase, weekly visits at the local physician's office are required during 1st cycle of therapy with a review of constitutional symptoms and physical exam, including transfusion requirement. During 2nd and 3rd cycles visits are every 4 weeks, and then every 3 months thereafter. All examinations will include body weight. On Day 1 of Cycle 1, before PK/PD blood-draws, the vital signs will be done as well as with the physical exams. On all other clinical visits vital signs are taken once. Overall response assessments will be graded according to consensus criteria for treatment response.

- d. Overall response assessments are required on Day 1 of Cycles 2, 3, and 4 and then every 3 months thereafter. If the dose of INCB018424 is escalated to 50 mg BID after cycle 1, then overall response assessments are required on Day 1 of Cycles 3, 4, and 5 and then every 3 months thereafter.
- e. ECOG performance criteria must be 0, 1 or 2 at screening. ECOG assessment is required on Day 1 of 2nd and 3rd cycles and thereafter every scheduled subsequent visit on Day 1.
- f. All medications received within 30 days prior to the Screening Visit are to be recorded. Reassessments will be done weekly at the local physician's office during 1st cycle of therapy and then every 4 weeks during 2nd and 3rd cycles and thereafter every 3 months during scheduled visits.
- g. Serum chemistry (Sodium, potassium, chloride, CO₂, blood urea nitrogen, creatinine, glucose, calcium, phosphate, magnesium, AST or ALT, total bilirubin, alkaline phosphatase, total protein, albumin, uric acid, lactic dehydrogenase) is required every week during the 1st cycle and every two weeks during Cycles 2 and 3, and at each scheduled subsequent visit. Urinalysis is required only at screening and at the end of study visit. Hepatitis serology and HIV laboratory test will be performed only during the Screening Visit if there are no results available from past 3 months. A pregnancy test will be obtained at screening. Urine pregnancy test will then be performed if there is a suspicion of pregnancy. A serum pregnancy test will be performed to confirm positive results obtained from a urine test. FSH test will only be performed on females who have been amenorrheic for >1 year, and if levels are elevated no further pregnancy testing is required for these female patients.
- h. Complete blood count (CBC) including absolute neutrophil count and platelet count are required weekly for Cycle 1, 2 and 3 and every two weeks for subsequent visits.
- i. Bone marrow aspiration or biopsy will be taken during the screening phase (within 4 weeks of starting drug), and at start of Cycle 4 (± 7 days), Cycle 7 (± 7 days), and thereafter at start of each 6th subsequent cycle (+/- 7days). Evaluation will include staining for fibrosis and cytogenetics if abnormal prior to therapy. Cytogenetic studies will be repeated only in patients with abnormalities at baseline, on Day 1 of Cycles 4 and 7 and thereafter on Day 1 of each 6th subsequent cycle(+/-7days). If unable to obtain BM aspirate, cytogenetics may also be done on peripheral blood collected for PD/PK analysis.
- j. Instruct patient that the dose is to be taken at 12 hour intervals at approximately the same time each day. The first dose of each day should be taken in the morning.
- k. For Cycle 1, PK samples to be collected on Day 1 at pre-dose, 0.5, 1, 1.5, 2, 4, 6, and if possible 8 hours after administration of the morning dose of INCB018424. For Cycles 2 and 3, a PK sample will be collected at pre-dose on Day 1.
- I. For Cycle 1, plasma and whole blood PD samples will be collected on Day 1 at pre-dose and 2, hours after administration of the morning dose of INCB018424. For Cycles 2, 3, and each subsequent scheduled visit to MDACC, plasma and whole blood PD samples will be collected at pre-dose on Day 1. Final PD sample will be collected at End-Of–Study visit. Not all samples may be collected on all patients. See Appendix F.
- m. Adverse events (AEs) considered related to study medication must be followed until resolution, start of a different treatment therapy or no longer considered to be clinically relevant in the opinion of the investigator. During the treatment phase, AE assessment is required weekly at the local physician's office during 1st cycle of therapy. During the 2nd and 3rd cycles assessments are required every 4 weeks, and then every visit thereafter.
- n. Compliance should be checked at each scheduled clinical visit. Any unused drug in sealed bottles will be returned to Incyte or its designee. MDACC will follow internal procedures to destroy and dispose of unused drug in open/unsealed bottles.

Protocol Number 2007-0925 October 13, 2008 Page 17 of 36

o. End-of-Study procedures are to be completed if patient completes study or at anytime patient terminates treatment early in the study.

5.2.1 Cycle 1

5.2.1.1 Cycle 1 - Day 1

Patients who meet all of the study entrance criteria and none of the exclusion criteria will return to the study site on Day 1. The following procedures will be performed:

- Review of eligibility criteria including laboratory results.
- Review of prior/concomitant medications.
- Targeted physical examination.
- Record vital signs.
- Intercurrent illness will be assessed pre-dose.
- Administration of the 1st dose of the INCB018424.
- Blood samples for plasma PK assessment will be drawn pre and postdose with exact time recorded as defined in the Study calendar. PK samples to be collected on Day 1 at pre-dose, 0.5, 1, 1.5, 2, 4, 6, and if possible 8 hours after administration of the morning dose of INCB018424. If not feasible, all samples do not have to be drawn in all patients.
- Blood sample for plasma and whole blood PD will be collected pre-dose, and 2 hours after administration of the morning dose of INCB018424.
- Adverse events will be assessed post-dose.
- Study medication for the first Cycle will be dispensed and the Study staff will instruct the patient regarding dosing regimen.
- Patients will be instructed to call the Investigator or designated research staff if they experience any "troubling" signs and/or symptoms that are of moderate or greater severity.
- Patients will be asked to return to the clinical site on Day 8. Patients will be asked to bring the study medication.

5.2.1.2 Days 2 to 7

Patients will self-administer study medication as instructed twice daily at approximately 12 hour intervals in an out-patient setting.

5.2.1.3 Day 8 ± 2

The following procedures will be performed:

- Review of medical history and concomitant medication.
- Review of any adverse events.
- Targeted physical examination and vital signs.
- Blood sampling for blood serum chemistry tests, CBC with Differential, ANC, platelet count
- Review all safety information and criteria for dosing interruptions to determine if patients should receive further doses.

- Patients will be instructed to call the Investigator or designated research staff if they experience any "troubling" signs and/or symptoms that are of moderate or greater severity.
- Patients will be asked to return to the clinical site on Day 15.

5.2.1.4 Days 9 to 14

Patients will self-administer study medication as instructed twice daily at approximately 12 hour intervals in an out-patient setting.

5.2.1.5 Day 15 ± 2

The following procedures will be performed:

- Review of medical history and concomitant medication.
- Review of any adverse events.
- Targeted physical examination and vital signs.
- Blood sampling for blood serum chemistry tests, CBC with Differential, ANC, platelet count
- Patients will be instructed to call the Investigator or designated research staff if they experience any "troubling" signs and/or symptoms that are of moderate or greater severity.
- Patients will be asked to return to the clinic on Day 22.
- Review all safety information and criteria for dosing interruptions (Section 10.4) to determine if patients should receive further doses.

5.2.1.6 Days 16 to 21

Patients will continue to self-administer study medication per instructions twice daily at approximately 12 hour intervals in an out-patient setting.

5.2.1.7 Day 22 ± 2

The following procedures will be performed:

- Review of medical history and concomitant medication.
- Review of any adverse events.
- Targeted physical examination and vital signs.
- Blood sampling for the blood serum chemistry tests, CBC with Differential, ANC, platelet count
- Patients will be instructed to call the Investigator or designated research staff if they experience any "troubling" signs and/or symptoms that are of moderate or greater severity.
- Patients will be asked to return to the clinic on Day 1 of Cycle 2 (Day 28 to 31 of Cycle 1). Patients will be asked to bring all study medication with them to the visit.

- Due to PK and PD samples being collected at the next visit, patients will be asked to withhold their morning dose of study medication on Day 1 of Cycle 2.
- Review all safety information and criteria for dosing interruptions (Section 10.4) to determine if patients should receive further doses.

5.2.1.8 Days 23 to 27

Patients will continue self-administering study medication per instructions twice daily at approximately 12 hour intervals in an out-patient setting.

5.2.2 Cycles 2 and 3

